- Incidence of medications with possible antiviral activity (hydroxychloroquine, lopinavir/ritonavir, ribavirin or remdesivir) or adjunctive therapy use (e.g., tocilizumab)
- Incidence (and length in days) of extracorporeal membrane oxygenation use
- Incidence (and length in days) of renal replacement therapy use
- Intolerance of high dose (50mg) losartan after tolerating 25mg
- Change in SARS-CoV-2 viral load determined by quantitative PCR

Inclusion criteria:

1. Age ≥ 18 years admitted to the University of Kansas Health System.
2. Confirmation of infection with SARS-CoV-2 by PCR testing.
3. Hypoxic respiratory failure
 - Requiring mechanical ventilation or oxygen OR a SpO₂ $\leq 94\%$ on room air or a P_aO₂/F_iO₂ (P/F) ratio <300 OR tachypnea (respiratory rate ≥ 24 breaths/min).
4. Other concomitant medications such as antivirals and hydroxychloroquine are allowed.
5. Participants prescribed standard of care (SOC) losartan (25mg QD) within 48 hours of consenting may be considered for enrollment if eligibility criteria are met based on EMR data assessment, i.e. no other ARB or ACE prior to SOC medication administration. If participant is eligible and signs consent form, investigational losartan 25mg QD will be ordered to replace SOC prescription on the following scheduled dose.

Exclusion criteria:

1. Pregnancy.
2. Respiratory failure due to a process other than COVID-19.
3. Intolerance to ARBs.
4. Previous treatment with an ARB or ACE inhibitor (see exception in inclusion criteria).
5. Current chronic use of medication with known interactions with losartan including NSAIDs (intermittent prior use is acceptable), potassium supplementation aliskiren.
6. Blood pressure less than 90 mm Hg systolic or 60 mm Hg diastolic recorded on at least two readings 30 min apart.
7. Need for vasopressors, unless norepinephrine ≤ 0.1 μ g/kg/min
8. Hyperkalemia (serum K⁺ > 5.5 mM).
9. Known cardiac failure (left ventricular ejection fraction $\leq 35\%$), renal insufficiency (Cockcroft-Gault < 30 mL/min/1.73 m² or urinary output < 20 mL/h), hepatic failure (LFTs > 5 x normal upper limit).
10. Known renal artery stenosis.
11. Neurological, psychiatric, endocrine or neoplastic diseases that are judged to interfere with participation in the study.
12. On another interventional trial (including one for COVID-19) that excludes participation.
13. Meeting all inclusion criteria for more than 48 hours prior to Day 0

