Patients and/or surrogate decision maker who do not give consent to treatment will be asked to allow collection of data from their medical record for use as a control group. Patients or surrogate decision makers who cannot consent in person, will be consented in accordance to the KUMC remote consent guidelines.

Parameters to be collected:

General: Demographics, clinical symptoms, history of other medical conditions, routine blood work, and concomitant medications. Baseline characteristics will include age, sex, race, ethnicity and body mass index, Simplified Acute Physiology Score (SAPS) II, National Early Warning Signs (NEWS), Sequential Organ Failure Assessment (SOFA) and acute physiology and chronic health evaluation (APACHE) II. The APACHE II will be collected only for participants admitted in the ICU.

Physical examination: We will record vital signs such as highest and lowest temperatures (°C), highest respiratory rate, highest heart rate, lowest mean arterial pressure (mmHg), highest oxygen requirements and body mass index (BMI).

Confirmation of infection with SARS-CoV-2 by PCR testing by chart. Also, documentation of other infections if present.

Blood samples: We will collect laboratory values throughout the study (hemoglobin, platelet count, white blood cell count, lymphocyte count, liver enzymes, glucose, blood urea nitrogen, creatinine, creatine kinase, lactate, and arterial blood gas) and as indicated (LDH, ferritin, troponin), potassium and other values available in EMR. Store plasma at beginning and at the end of study for later analysis (possibly IL-6 etc.).

Nasopharyngeal swabs: We will collect nasopharyngeal swabs at study enrollment and end of study to determine SARS-CoV-2 viral load by quantitative PCR.

Radiographic imaging will be recorded upon presentation and subsequently thereafter as indicated.

Monitor for deteriorating acute respiratory failure and determine the indication the need for mechanical ventilation.

Study procedures (see schematic)

Day 0

- Labs collected for routine clinical care and the medical record will be reviewed to screen for eligibility. Assuring pre-menopausal women have a negative pregnancy test.
- Consenting participants who meet enrollment criteria will be started on losartan 25 mg once daily per mouth.
- Treatment group will have nasopharyngeal swab and research plasma collected for analysis.
- Control group will be followed only for data collection until study completion.

Day 1-2:

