- Monitor subject for safety and losartan stoppage criteria.
- For participants following inclusion criteria #5: Day 0 assessments should be performed on enrollment day as well as day 1 **or** day 2 based on first dose of SOC losartan administration.

Day 3:

- Dose escalation: On study day 3 if none of the parameters listed below are met the dose of losartan will be increased to 50 mg once daily.

Day 4 until study completion:

- Monitor subject for safety and losartan stoppage criteria.
- Treatment group will have nasopharyngeal swab and research plasma collected at end of study.

Stoppage criteria for losartan

- Hyperkalemia (persistent values >5.5 mM recorded on at least 2 readings).
- Worsening renal function (Cockcroft-Gault <30 mL/min/1.73 m²) or urinary output <20 mL/h.
- Skin rashes, palpitations or other moderate or severe adverse events (interference with usual daily activities) without clear explanation should warrant immediate cessation of treatment and notification of study personnel.
- Development of sustained hypotension defined as SBP <90 mmHg, DBP <60 mmHg recorded on at least two readings 30 min apart or use of norepinephrine >0.1 µg/kg/min.

[figure not shown]
- Any change in monitor lab parameters deemed significant and potentially related to study drug by the Investigator.

Dose de-escalation criteria

- Any change in monitoring parameter after dose increase from 25 mg to 50 mg that is considered significant by the investigator will trigger a decrease dose back to 25 mg
- If abnormal parameter is resolved and, in the opinion of the investigator, is unlikely to be related to losartan will increase dose back to 50 mg
- If de-escalation criteria is met after re challenging 50mg dose, the dose will be once more decreased to 25mg until the end of the study.

Criteria for resuming after stopping

- If stoppage criteria have resolved and reason for stoppage is felt to be unlikely or possibly related to losartan, discussion of resumption of losartan with medical monitor
- Dose resumption will start at 25 mg. If stopped at 25 mg → the dose will be continued for three days followed by increase to 50 mg if tolerated. If stopped at 50 mg, 25 mg will be started and escalated to 50 mg the day after if tolerated.

Control

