Hemoglobin	Hemoglobin (Hgb) <LLN - 10.0 g/dL; <LLN - 6.2 mmol/L; <LLN - 100 g/L Follow up	Hgb <10.0 - 8.0 g/dL; <6.2 - 4.9 mmol/L; <100 - 80g/L ; follow up	Hgb <8.0 - 6.5 g/dL; <4.9 - 4.0 mmol/L; <80 - 65 g/L; transfusion indicated; stop losartan, follow up	Life-threatening consequences; urgent intervention indicated; stop losartan	Death
Leukocytes	<LLN - 3000/mm3; <LLN - 3.0 x 10e9 /L; follow closely	<3000 - 2000/mm3; <3.0 - 2.0 x 10e9 /L; stop losartan; follow up	<2000 - 1000/mm3; <2.0 - 1.0 x 10e9 /L; stop losartan; follow up and further investigation	<1000/mm3; <1.0 x 10e9 /L; stop losartan; follow up and further investigation	
Platelets	<LLN - 75,000/mm3; <LLN - 75.0 x 10e9 /L; follow closely	<75,000 - 50,000/mm3; <75.0 - 50.0 x 10e9 /L; follow closely, stop losartan	<50,000 - 25,000/mm3; <50.0 - 25.0 x 10e9 /L; follow closely, stop losartan,	<25,000/mm3; <25.0 x 10e9 /L; follow closely, stop losartan, transfer to ICU	
Angioedema	N/A	N/A	Angioedema occurs – mild: stop losartan, transfer to ICU	Angioedema occurs – severe tongue swelling: stop losartan, transfer to ICU	Death
Hypotension (for participants in ICU on sedation for mechanical ventilation ONLY)	Initiation of vasopressors	Increase in vasopressor dose to >0.1; stop losartan, follow up	Persistent hypotension without alternative cause; stop losartan, follow up	Irreversible end organ damage related to hypotension; stop losartan, follow up	Death
Hypotension (for participants NOT in ICU on sedation for mechanical ventilation)	Asymptomatic, intervention not indicated	Non-urgent medical intervention indicated; stop losartan, follow up	Urgent medical intervention or transfer to ICU indicated; stop losartan, follow up	Life-threatening and urgent intervention indicated; losartan, follow up	Death

Creatinine	>1 - 1.5 x baseline; >ULN - 1.5 x ULN; follow up	>1.5 - 3.0 x baseline; >1.5 - 3.0 x ULN; close follow up	>3.0 baseline; >3.0 - 6.0 x ULN; stop losartan, nephrology intervention	>6.0 x ULN; stop losartan, nephrology intervention	
Potassium&	>ULN to 5.5 mmol/L; monitor	>5.5 - 6.0 mmol/L; stop losartan, close follow up	>6.0 - 7.0 mmol/L; urgent intervention indicated, stop losartan, intervention	>7.0 mmol/L; life-threatening consequences; stop losartan, intervention	

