AST, ALT, alkaline phosphatase	>ULN - 3.0 x ULN; monitor closely	Asymptomatic with AST, ALT, alk.P. >3.0 - 5.0 x ULN; >3 x ULN with the appearance of worsening of fatigue, nausea, vomiting, right upper quadrant pain or tenderness, fever, rash, or eosinophilia or bilirubin elevation; stop losartan, monitor	>5.0 - 20.0 x ULN; >5 x ULN for >2 weeks; stop losartan, monitor	>20.0 x ULN; stop losartan, monitor, other interventions	
CPK#	>ULN - 2.5 x ULN; monitor closely	>2.5 x ULN - 5 x ULN; stop losartan, monitor closely	>5 x ULN - 10 x ULN; stop losartan, monitor closely	>10 x ULN; stop losartan, monitor closely, possible admission with other abnormalities	

& Given that hyperkalemia occurs with patients on Losartan and there could be patients with renal dysfunction that falls just under the 1.5 mmol/L creatinine exclusion point, the DMC would recommend a modification to the reporting of abnormal results of serum potassium. We suggest that upon receipt of a level greater than 5.5 mM, the blood draw be repeated within 24 hours and that the PI for the study respond to the repeat level by either reassuring the patient that all is well or if the level is still rising discontinuing the study drug. Since there will be blood draws frequently during this study, we feel that continuing the study subject on study drug if the level returned to normal on repeat testing is safe, especially in the expected monitored setting.

Only done when clinically indicated

Pregnancy

Female subjects will be tested for pregnancy by hospital policy. If pregnant they will be excluded.

It is not expected that a female subject becomes pregnant while participating in the study. In the rare case this does occur, study drug must be stopped immediately and permanently discontinued. Losartan does not have effects on a fetus in the 1st trimester but could later on. The investigator must notify the DSMB and IRB within 24 hours of the site's knowledge of the subject's pregnancy and other agencies as by law. Pregnancy itself does not constitute an AE. Pregnancy test will be performed at all site visits.

Data monitoring plan will be implemented as follows:

- Safety monitoring will be done:
 - All SAEs attributable to study drug will be reported to the study investigator(s) and discussed with an internal safety and monitoring group of 5 experts consisting of an intensivist(s), infectious disease specialist(s), ethicist and biostatistician. These experts may not report to the PI directly.

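### Table 1 stops losartan at laboratory values that eligibility allows at entry, and the plan does not say which rule governs a single high potassium value or a drug-related change at 50 mg

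*Combined protocol and SAP*

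**What the plan says.** **Entry.** Under Study procedures, Day 0: "Consenting participants who meet enrollment criteria will be started on losartan 25 mg once daily per mouth". The laboratory exclusions are potassium above 5.5 mM, Cockcroft-Gault below 30, and, in exclusion criterion 9, "hepatic failure (LFTs > 5 x normal upper limit". No limit is set for leukocytes, platelets, haemoglobin or CPK.

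**Table 1.** The table attaches actions to grades:

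- Liver tests, Grade 2: the cell opens "Asymptomatic with AST, ALT, alk.P. >3.0 - 5.0 x ULN" and ends with an instruction to stop.
- Leukocytes, Grade 2: "<3000 - 2000/mm3; <3.0 - 2.0 x 10e9 /L; stop losartan; follow up".
- Platelets, Grade 2: "<75,000 - 50,000/mm3; <75.0 - 50.0 x 10e9 /L; follow closely, stop losartan".
- Haemoglobin, Grade 3 (below 8.0 g/dL): "transfusion indicated; stop losartan, follow up".
- CPK, Grade 2: ">2.5 x ULN - 5 x ULN; stop losartan, monitor closely". A note under the table says a test is done only on clinical indication. I take it to be the CPK note.

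**Potassium.** The stoppage list reads "Hyperkalemia (persistent values >5.5 mM recorded on at least 2 readings". The Table 1 cell stops losartan from just above 5.5 mmol/L without asking for a second reading. Its footnote, phrased as a monitoring committee suggestion, asks for a repeat within 24 hours. It would discontinue if the level is still rising and continue if it is back to normal.

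**50 mg.** The stoppage list includes any laboratory change that the investigator finds significant and potentially drug-related. The de-escalation criteria send any significant change after the increase back to 25 mg. Intolerance of 50 mg after tolerating 25 mg is a secondary endpoint.

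**Adverse events.** The definition covers events during the study and takes in both the Table 1 monitoring data and the stoppage criteria.

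**The concern.** These rules decide who stays on drug and at what dose. They also feed the safety result: Table 1 findings and stoppage criteria count as adverse events, and the sample size section judges losartan against controls on total AE/SAEs with a 20% allowance either way. Where two rules give different instructions for one value, clinicians can treat identical patients differently while each follows the protocol. The same values may also be counted as events in one patient and ignored in another. Controls identified retrospectively sign no consent form, although event collection is said to begin at consent, so a shared rule for values already abnormal at the start matters in both groups.

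**Working it through.** The plan gives no figure to reproduce here. The check sets the rules side by side and applies them to example values.

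**1. Entry range against Table 1 stop**

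| Row | Entry limit | Table 1 stop begins | Example: eligible, yet meets a stop |
|---|---|---|---|
| AST/ALT/alk. phos. | excluded above 5 x ULN | above 3 x ULN | 4 x ULN |
| Leukocytes | none | below 3000/mm3 | 2500 |
| Platelets | none | below 75,000/mm3 | 60,000 |
| Haemoglobin | none | below 8.0 g/dL | 7.5 |
| CPK (when measured) | none | above 2.5 x ULN | 3 x ULN |
| Potassium | excluded above 5.5 | above 5.5 | none; the limits match |
| Creatinine | Cockcroft-Gault below 30 | above 3 x baseline or above 3 x ULN | not counted |

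In 5 of 7 rows the stop lies inside the eligible range, and none of those 5 refers to baseline. The creatinine row has a baseline limb and a ULN limb, so it does not settle how baseline is handled.

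**2. Potassium, first value then repeat**

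| Values | Potassium item in stoppage list | Table 1 cell | Footnote |
|---|---|---|---|
| 5.8 then 4.8 | no stop required | stop | continue |
| 5.8 then 5.7 | stop | stop | no action given |
| 5.8 then 5.9 | stop | stop | stop |
| 6.4 then 5.0 | no stop required | stop, urgent intervention | continue |
| 6.4 then 6.2 | stop | stop | no action given |

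If the footnote is taken to modify the cell, it agrees with the list for 5.8 then 4.8. Where the repeat stays above 5.5, list and cell agree and the footnote is merely silent or concurs. The row that remains is 6.4 then 5.0. The footnote has no upper limit, so it would let dosing continue after a value for which the cell demands a stop and urgent intervention.

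**3. Change at 50 mg**

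Take platelets of 60,000, judged significant and potentially related:

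- Laboratory-change item in the stoppage list: stop.
- Table 1, Grade 2: stop.
- De-escalation criteria: reduce to 25 mg.

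No precedence is stated, and the routes back differ. After a stop, an unlikely or possibly related event can be resumed following discussion with the medical monitor. After a step-down, return to 50 mg requires that a relation to losartan be unlikely. The endpoint of 50 mg intolerance does not say whether a stop, a step-down or both count.

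**The case against.** The strongest reply is that Table 1 is an adverse event grading table and an adverse event must arise during the study. On that view an unchanged entry value is not an event and triggers nothing. This is a reasonable reading and it removes the entry problem, but the plan does not state it for any of the five rows.

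A reader might infer that eligible patients would necessarily be started and stopped on the same blood sample, or have the dose raised on day 3 against a stop. The documents do not support that as a certainty. The day 3 condition points to parameters further down, which could include Table 1. The side-effects section stops losartan for moderate or severe events without another clear explanation, and Grade 2 is defined as moderate. If a stable AST of 4 x ULN is an event and unexplained, it is stopped there too; if it is not an event, neither source stops it.

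On potassium, the footnote does reconcile most cases. Even for 6.4 then 5.0, investigator discretion or the rule on unexplained severe events could lead to a stop. What stands is that the rule written specifically for potassium does not require one.

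At 50 mg, stopping for related changes and stepping down for others is workable, and the different return conditions may reflect different oversight. The order is nevertheless unstated. A reader might also try to express the choice of route as milligrams of losartan. That needs an event day, a resolution day and the medical monitor's decision, none of which the documents give, and the total could fall either way.

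Inpatient dosing, investigator discretion, the medical monitor and DSMB reviews after 5 and 25 patients limit harm. They do not say which rule governs.

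**Conclusion.** The concern holds in three limited parts.

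- Five Table 1 stops overlap the entry range, and the plan is silent on baseline.
- Potassium rules conflict most clearly for a first value above 6.0 that normalises.
- Stop and step-down overlap at 50 mg without precedence, so a named secondary endpoint is undefined.

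The count of 5 of 7 is a count of rows, not of patients. The documents give no frequency for such values; each affected participant would be 1/50 = 2% of the treated group. No direction of bias in the adverse event comparison can be claimed. The figure within the stoppage section and the separate DSMB charter were not available to me and might resolve part of this. I rate the point minor to moderate: the rules disagree on safety actions that feed the primary comparison, but the safeguards are real and the remedy is small.

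**What to change.** 1. Keep every existing stop (Cockcroft-Gault, urine output, rash and palpitations, blood pressure, norepinephrine). Add Table 1 as a further set of stops and say that it also applies to the day 3 increase. Table 1 should not replace the list, because it lacks several of these criteria.
2. State that the liver, leukocyte, platelet, haemoglobin and CPK stops apply to worsening from baseline grade. The alternative is to align the entry limits with the stops.
3. Potassium above 5.5 and up to 6.0: repeat within 24 hours, say whether the dose is held meanwhile, and stop if still above 5.5. Above 6.0: stop at once. The clinical team and DSMB should confirm the 6.0 level. Replace the footnote, which also cites a creatinine exclusion that the exclusion criteria do not contain.
4. At 50 mg: stop for a potentially related change, otherwise step down. Count either action as 50 mg intolerance when the change is judged potentially drug-related.
5. Count a laboratory adverse event only when it is new or worse in grade than baseline, identically in treated and all control patients.

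The cost is amendment text. Baseline grades use laboratory values already collected, although CPK may be missing where it was not indicated. The downside of item 2 is continued dosing at stable abnormal entry values, which the clinical team and DSMB should accept explicitly. Tighter entry limits avoid that but could slow accrual.

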Thus, good evidence suggests that at least acute treatment with ARBs could ameliorate lung injury in COVID-19. We therefore propose to test losartan in a Phase I proof of concept and safety trial. The primary hypothesis to be tested is that losartan treatment is safe in the setting of acute SARS-CoV-2 infection. Secondarily, losartan can potentially reduce the length of respiratory failure due to SARS-CoV-2.

Significance

Importance of the problem: As outlined above, there is currently no data that supports specific treatment options for respiratory failure in COVID-19. There are active or soon to be active clinical trials that may show promise in this space such as blocking IL-6 with tocilizumab²⁰ or using hydroxychloroquine. None of these therapies are without side effects and alternative or additional approaches could lessen the burden of respiratory failure in this patient population.

Approach and Protocol

This is an open label, phase 1 clinical trial to evaluate the safety of losartan in respiratory failure due to COVID-19.

Clinical Trial setup:

Detailed inclusion and exclusion criteria are listed below. Briefly, 50 patients with COVID-19 and respiratory failure who meet criteria and agree to participation in the study will be placed on losartan 25 mg daily on study day 0. If parameters are met the dose of losartan will be increased to 50 mg on study day 3. Participants will continue losartan until they experience resolution of respiratory failure (normal oxygen levels on room air), are discharged from the hospital, meet stoppage criteria (detailed below) or complete 14 days of therapy.

Primary hypothesis and endpoint:

- Losartan is safe in acute respiratory failure due to SARS-CoV-2.

Secondary endpoints:

- Losartan reduces the number of days on supplemental oxygen in respiratory failure due to COVID-19
- Incidence of mechanical ventilation use
- Days on mechanical ventilation
- Incidence of non-invasive positive pressure ventilation or heated high flow nasal cannula use
- Days on non-invasive positive pressure ventilation or high flow nasal cannula
- Incidence of transfer to ICU from non-ICU hospital bed
- ICU length of stay (days)
- In-hospital mortality
- Hospital length of stay (days)
- Cumulative incidence of severe adverse events
- Cumulative incidence of adverse events
- Change from baseline in oxygenation

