Patients that request to not be treated with Losartan will be approached by the study team to request permission for their standard of care treatment and data be followed and recorded by the research team for this study. Patients that agree, will sign the consent form, but will not provide a blood sample for research. We will also collect medical information relating to safety criteria on historical controls treated at the University of Kansas Hospital in the 30 days prior to the study start date (3/25/2020) and during the study period. These controls will be retrospectively identified through query of the electronic health record. We will attempt to include controls that meet all criteria for enrollment into the study but to achieve a ratio of controls to study participants of 2:1 may need include some with exclusion criteria (excluding prior ACE inhibitor or ARB use). Controls identified retrospectively will not undergo informed consent as this represents minimal risk.

Losartan

Losartan is an FDA-approved ARB widely prescribed for treatment of hypertension, heart failure, and for renal protection in patients with diabetes. The doses proposed in this study are well tolerated by non-hypertensive patients without significant effect on blood pressure. The proposed starting dose of losartan is 25 mg orally per day with increase to 50 mg orally per day on day 3 if tolerated until they patient is discharged from the hospital, met stoppage criteria (above) or completed 14 days of therapy.

The most common side effects are fatigue and dizziness. Serious adverse events that are rare include angioedema, hypotension, renal dysfunction or failure, blood dyscrasias, hepatitis, or rhabdomyolysis. The following are meant to mitigate risk to the subjects: Dosing will be done in an inpatient setting with clinically indicated close observations of blood pressure and organ dysfunction (blood work). Subjects with hyperkalemia, renal dysfunction, or who are taking potassium supplements will not be enrolled into the study. Participants will be given written descriptions of potential side effects and potential responses to the side effects.

Sample size and Statistics

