- Fatal (death, regardless of cause, that occurs during participation in the study or occurs after participation in the study and is suspected of being a delayed toxicity due to administration of the study drug)
- Life-threatening, such that the subject was at immediate risk of death from the reaction as it occurred
- Inpatient hospitalization or prolongation of hospitalization

- Persistent or significant disability/incapacity (disability is defined as a substantial disruption of a person's ability to conduct normal life functions)
- Congenital anomaly or birth defect
- Important medical event that, based upon appropriate medical judgment, may jeopardize the subject or may require medical or surgical intervention to prevent 1 of the outcomes listed above (e.g., an allergic bronchospasm requiring intensive treatment)

Data Safety and Monitoring Plan and Internal DSMB

Anticipated Adverse Events and Grading Scale

Losartan side effects: The most common side effects are fatigue and dizziness. Serious adverse events that are rare include angioedema, hypotension, renal dysfunction or failure, blood dyscrasias, hepatitis, or rhabdomyolysis (clinical assessment of muscle pain). Skin rashes, palpitations or other moderate or severe adverse events without other clear explanation warrants immediate cessation of treatment and notification of study personnel, who will take appropriate reporting actions.

Grading Scale

Grade 1:

Mild; asymptomatic or mild symptoms; clinical or diagnostic observations only; intervention not indicated.

Grade 2

Moderate; minimal, local or noninvasive intervention indicated; limiting age-appropriate instrumental ADL*Grade 3

Severe or medically significant but not immediately life-threatening; hospitalization or prolongation of hospitalization indicated; disabling; limiting self care ADL**.

Grade 4

Life-threatening consequences; urgent intervention indicated.

Grade 5

Death related to AE.

Activities of Daily Living (ADL)

* Instrumental ADL refer to preparing meals, shopping for groceries or clothes, using the telephone, managing money, etc.

** Self-care ADL refer to bathing, dressing and undressing, feeding self, using the toilet, taking medications, and not bedridden.

Table 1

Adverse event	Grade 1	Grade 2	Grade 3	Grade 4	Grade 5

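### An adverse event that ends losartan also ends study participation, so later adverse events can be lost from the losartan side only of the ±20% safety comparison

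*Combined protocol and SAP*

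**What the plan says.** **Withdrawal and AE collection.** Removal of Subjects from Study equates withdrawal with leaving the study, not only the drug. Its mandatory list includes an AE or SAE that the investigator or the patient considers to require ending treatment. Patients who leave are not replaced, and are asked to allow follow-up off drug. Safety Reporting adds a discretionary withdrawal from the study for intolerance. Definition of an Adverse Event sets the collection window, for both groups, from consent to completion of participation. The SAE definition keeps one later event in scope: a death that "occurs after participation in the study and is suspected of being a delayed toxicity due to administration of the study drug".

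**Controls.** Consented controls are followed for data until study completion (Study procedures, Day 0). Retrospective controls come from a query of the health record and give no consent (Control).

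**Criterion.** Sample size and Statistics would regard losartan as equivalent or superior on a ±20% difference in total AE/SAEs, with historical controls matched 2:1. It does not say whether 20% is relative or absolute, or whether events or patients are counted.

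**Dose rules.** Stoppage criteria for losartan include "Any change in monitor lab parameters deemed significant and potentially related to study drug by the Investigator". Dose de-escalation criteria then reduce to 25 mg for "Any change in monitoring parameter after dose increase from 25 mg to 50 mg that is considered significant by the investigator". Clinical Trial setup has patients continue losartan until they, among other end points, "meet stoppage criteria (detailed below) or complete 14 days of therapy"; the Losartan section repeats this with "met stoppage criteria (above) or completed 14 days of therapy".

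**The concern.** Safety is the primary question, and it is assessed on an AE total. The withdrawal rule ties stopping the drug for harm to leaving the study, so AE collection becomes optional in the patients who tolerated losartan worst. No control can leave on these grounds. AEs lost this way would therefore lower one side of the comparison only.

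A smaller matter concerns dosing. At 50 mg, a lab change that is significant and possibly drug-related meets both the stop trigger and the reduce trigger, and the readable text does not rank the two.

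**Working it through.** The plan gives no AE rate, withdrawal rate, alpha or power, so there is no figure of its own to reproduce. From the documents: 50 treated patients, at most 14 days of losartan, a ±20% margin. Everything else below is assumed and labelled so.

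**1. Who can be lost, and by which route**

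| Ground for leaving | Losartan | Consented controls | Retrospective controls |
|---|---|---|---|
| AE/SAE requiring end of treatment (mandatory) | yes | cannot apply | cannot apply |
| Intolerance to study drug (discretionary) | yes | cannot apply | cannot apply |
| Own request | yes | yes | no such step |

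The first two rows are specific to losartan. After either, further AEs are collected only if the patient agrees. Three things are not lost: the triggering AE itself, events after a temporary stop (the protocol provides for resumption), and later deaths suspected to be delayed toxicity.

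**2. How much loss would matter**

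Assume ±20% is a relative difference in AEs per patient. Let R be the true treated-to-control ratio and s the share of treated AEs not collected. The observed ratio is R(1 − s), which falls to 1.20 when s = 1 − 1.20/R. With 50 treated patients and c AEs per control patient (assumed 1 to 3), the number of uncollected AEs is 50 × c × (R − 1.20).

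| True R (assumed) | s | AEs, c = 1 | AEs, c = 3 |
|---|---|---|---|
| 1.25 | 1 − 1.20/1.25 = 4.0% | 2.5 | 7.5 |
| 1.30 | 1 − 1.20/1.30 = 7.7% | 5 | 15 |
| 1.40 | 1 − 1.20/1.40 = 14.3% | 10 | 30 |

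**3. What withdrawals could produce such a loss**

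Assume a share f of treated patients leaves for an AE on day d, all of them decline follow-up, and AEs occur at a constant rate over 14 days. The share of observation lost is f × (14 − d)/14. The true ratio behind an observed 1.20 is 1.20 divided by (1 − that share).

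- f = 10%, d = 7: 0.10 × 7/14 = 5.0%; true ratio 1.26
- f = 20%, d = 4: 0.20 × 10/14 = 14.3%; true ratio 1.40
- f = 30%, d = 4: 0.30 × 10/14 = 21.4%; true ratio 1.53

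These are upper illustrations because every patient is taken to decline. With full agreement the loss is zero.

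**4. If the criterion counts patients with any AE**

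The triggering AE already classifies the patient, so later AEs change nothing. The exception is withdrawal for an intolerance that was not recorded as an AE.

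**5. The dose rules**

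Table 1 has 7 laboratory rows, so grades 2 to 4 give 7 × 3 = 21 cells. The action includes stopping losartan in 19 (for potassium, read with the footnote on repeat testing). The other two, haemoglobin grade 2 and creatinine grade 2, give follow-up only. This count does not cover collected tests without a Table 1 row, such as glucose or lactate.

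**The case against.** **On withdrawal.** The protocol does plan follow-up off drug, temporary stops are untouched, and the triggering event is counted. What remains is later AEs in patients who stop for good and also decline follow-up. No document supports a particular number of such patients. All of this stands, and it is why the loss is given as a threshold and not as an estimate.

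A reader might infer that the safety comparison as a whole is biased towards losartan. The documents do not support that. Treated patients are monitored prospectively against stoppage criteria, while retrospective controls are reconstructed from the record. That difference may raise AE capture under losartan and work the other way. Only the direction of this one component is known.

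**On the dose rules.** A reader might infer that an investigator may freely choose between 0 mg and 25 mg. That is too strong. Clinical Trial setup and the Losartan section both end treatment once a stoppage criterion is met. Anticipated Adverse Events and Grading Scale also says that "other moderate or severe adverse events without other clear explanation warrants immediate cessation of treatment", which reaches an unexplained grade 2 change because grade 2 is labelled moderate. The version under Stoppage criteria for losartan, "moderate or severe adverse events (interference with usual daily activities) without clear explanation should warrant immediate cessation of treatment", adds a daily-activities qualifier that a symptom-free lab change would not meet, so a mismatch of wording remains. A figure within the stoppage list is also missing from the readable text and could show the dosing flow. What stands is a request for clarification with little bearing on the AE comparison.

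**Conclusion.** The withdrawal point holds. As written, an AE that ends losartan must also end study participation, and intolerance may do so; from then on AE collection depends on the patient's agreement. This can remove AEs from the losartan count only, so the component favours losartan in the primary safety comparison.

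Its size cannot be derived from the documents. It is zero with full agreement to follow-up and essentially nil if patients with any AE are counted. On a relative per-patient reading of ±20%, uncollected shares of 4.0%, 7.7% and 14.3% would bring true excesses of 25%, 30% and 40% down to the limit. The wording of the criterion, total AE/SAEs, fits a count of events more naturally, but it is not defined. The net direction across all ascertainment differences is unknown.

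The change should be made because it is cheap and bears on the primary question. Confidence is medium, given the undefined margin and the unknown withdrawal rate. The overlap between stopping and de-escalation is a minor wording matter.

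**What to change.** **Main change.** Amend the mandatory AE/SAE ground in Removal of Subjects from Study, and the intolerance sentence in Safety Reporting, so that such an event ends losartan treatment only. Continue AE collection from the chart unless consent is withdrawn. Because the readable text gives no fixed end of collection, name one cut-off for all treated and control patients, for example day 14 or hospital discharge, whichever comes first. Retrospective controls have no consent date, so state the day from which theirs is counted.

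**Wording note.** Under Dose de-escalation criteria, state that any stoppage criterion or Table 1 action to stop losartan (for potassium, after the repeat test) overrides de-escalation, in line with Clinical Trial setup and the Losartan section.

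**Cost.** A protocol wording amendment with no new procedures, and slightly more chart follow-up for patients who stop losartan.
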